12.2.11. Planned Analyses

Two database locks are planned for the study. The first database lock and a blinded review of data will occur after all patients complete the Week 24 study visit. The final database lock and unblinded analysis will occur at the end of the study.

Unblinding details will be specified in the unblinding plan section of the SAP.

13. Informed Consent, Ethical Review, and Regulatory Considerations

13.1. Informed Consent

The investigator is responsible for ensuring that the patient understands the potential risks and benefits of participating in the study, including answering any questions the patient may have throughout the study and sharing in a timely manner any new information that may be relevant to the patient's willingness to continue his or her participation in the trial.

The ICF will be used to explain the potential risks and benefits of study participation to the patient in simple terms before the patient is entered into the study and to document that the patient is satisfied with his or her understanding of the risks and benefits of participating in the study and desires to participate in the study.

The investigator is responsible for ensuring that informed consent is given by each patient. This includes obtaining the appropriate signatures and dates on the ICF prior to the performance of any protocol procedures and prior to the administration of investigational product.

13.2. Ethical Review

Lilly or its representatives must approve all ICFs before they are submitted to the ERB and are used at investigative sites(s). All ICFs must be compliant with the International Conference on Harmonisation (ICH) guideline on GCP.

Documentation of ERB approval of the protocol and the ICF must be provided to Lilly before the study may begin at the investigative site(s). The ERB(s) will review the protocol as required.

Any member of the ERB who is directly affiliated with this study as an investigator or as site personnel must abstain from the ERB's vote on the approval of the protocol.

The study site's ERB(s) should be provided with the following:

- the current IB or package labeling and updates during the course of the study
- ICF
- relevant curricula vitae

13.3. Regulatory Considerations

This study will be conducted in accordance with:

1. consensus ethics principles derived from international ethics guidelines, including the Declaration of Helsinki and Council for International Organizations of Medical Sciences International Ethical Guidelines
2. the ICH GCP Guideline [E6]
3. applicable laws and regulations

The investigator or designee will promptly submit the protocol to the applicable ERB(s).

An identification code assigned by the investigator to each patient will be used in lieu of the patient's name to protect the patient's identity when reporting AEs and/or other trial-related data.

13.3.1. Investigator Information

Physicians with a specialty in RA will participate as investigators in this clinical trial.

13.3.2. Protocol Signatures

The sponsor's responsible medical officer will approve the protocol, confirming that, to the best of his or her knowledge, the protocol accurately describes the planned design and conduct of the study. After reading the protocol, each principal investigator will sign the protocol signature page and send a copy of the signed page to a Lilly representative.

Attachment 1. Protocol JAGS Study Schedule

Study Schedule, Protocol I4V-CR-JAGS

	Screening		Blinded, Placebo- Controlled Treatment Part A										Open-label Part B					Follow-up Part Ca
Visit	1	1a	2	3	4	5	6	7	8	9	10	11	12	13	14	15	ET	801
Week of Treatment			Base-line 0	1	2	4	8	12	14	16	20	24	28	32	40	52	Any week	
Days from Visit 2	-42 to -3 days		0	7 ± 2 days	14 ± 2 days	28 ± 2 days	56 ± 3 days	84 ± 3 days	98 ± 3 days	112 ± 3 days	140 ± 3 days	168 ± 3 days	196 ± 3 days	224 ± 5 days	280 ± 5 days	365 ± 5 days	Any day	28 ± 5 days after last dose
Informed consent	X																	
Clinical assessments:																		
History	X																	
Physical examination	X																	
Symptom-directed physical examination ^b			X	X	X	X	X	X	X	X	X	X	X	X	X	X	X	X
Previous therapy/previous RA therapy	X																	
Patient demographics	X																	
Height	X																	
Weight	X		X	X	X	X	X	X	X	X	X	X	X	X	X	X	X	X
Waist circumference	X							X			X				X			
Vital signs (BP and pulse)	X		X	X	X	X	X	X	X	X	X	X	X	X	X	X	X	X
Habits ^c	X																	
Electrocardiogram ^d	X																	
Inclusion/exclusion review for entry	X																	
Inclusion/exclusion review for enrollment			X															

Visit	Screening		Blinded, Placebo- Controlled Treatment Part A										Open-label Part B				ET	Follow-up Part Ca
	1	1a	2	3	4	5	6	7	8	9	10	11	12	13	14	15		
Week of Treatment			Base-line 0	1	2	4	8	12	14	16	20	24	28	32	40	52	Any week	
Days from Visit 2	-42 to -3 days		0	7 ± 2 days	14 ± 2 days	28 ± 2 days	56 ± 3 days	84 ± 3 days	98 ± 3 days	112 ± 3 days	140 ± 3 days	168 ± 3 days	196 ± 3 days	224 ± 5 days	280 ± 5 days	365 ± 5 days	Any day	28 ± 5 days after last dose
Administer PPD or QuantiFERON®-TB Gold or T SPOT® TB teste	X																	
Read PPD or QuantiFERON-TB Golde		X																
Chest x-rayf	X																	
Preexisting conditions	X		X															
Adverse events			X	X	X	X	X	X	X	X	X	X	X	X	X	X	X	X
Concomitant medications	X		X	X	X	X	X	X	X	X	X	X	X	X	X	X	X	X
Randomization			X															
IWRS	X		X	X	X	X	X	X	X	X	X	X	X	X	X	X	X	X
Investigational product dispensed			X ^g			X	X	X		X	X	X	X	X	X			
Investigational products returned and assess compliance				X ^h	X ^h	X	X	X	X ^h	X	X	X	X	X	X	X	X	
Tender/swollen joint count (68/66 joints)	X		X	X	X	X	X	X	X	X	X	X	X	X	X	X	X	X
Patient's assessment of pain visual analog scale			X	X	X	X	X	X	X	X	X	X	X	X	X	X	X	X
Patient global assessment of disease activity			X	X	X	X	X	X	X	X	X	X	X	X	X	X	X	X

	Screening		Blinded, Placebo- Controlled Treatment Part A										Open-label Part B					Follow-up Part Ca
Visit	1	1a	2	3	4	5	6	7	8	9	10	11	12	13	14	15	ET	801
Week of Treatment			Base- line 0	1	2	4	8	12	14	16	20	24	28	32	40	52	Any week	
Days from Visit 2	-42 to -3 days		0	7 ± 2 days	14 ± 2 days	28 ± 2 days	56 ± 3 days	84 ± 3 days	98 ± 3 days	112 ± 3 days	140 ± 3 days	168 ± 3 days	196 ± 3 days	224 ± 5 days	280 ± 5 days	365 ± 5 days	Any day	28 ± 5 days after last dose
Physician global assessment of disease activity			X	X	X	X	X	X	X	X	X	X	X	X	X	X	X	X
Hand and foot x-rays ⁱ	X ⁱ									X		X				X	X ⁱ	
HAQ-DI			X	X	X	X	X	X	X	X	X	X	X	X	X	X	X	X
Morning joint stiffness - diary			X ^k															
Morning joint stiffness - tablet ^l			X	X	X	X	X	X	X	X	X	X	X	X	X	X	X	X
FACIT-F			X			X	X	X		X	X	X	X	X	X	X	X	X
EQ-5D-5L			X			X	X	X		X	X	X	X	X	X	X	X	X
Worst tiredness NRS-diary			X ^k															
Worst tiredness NRS-tablet ^l			X	X	X	X	X	X	X	X	X	X	X	X	X	X	X	X
WPAI-RA			X		X	X	X	X		X	X	X	X	X	X	X	X	X
Worst joint pain NRS-diary			X ^k															
Worst joint pain NRS-tablet ^l			X	X	X	X	X	X	X	X	X	X	X	X	X	X	X	X
QIDS-SR16			X					X				X				X	X	X
Healthcare resource use			X			X	X	X		X	X	X	X	X	X	X	X	X
Laboratory tests																		
TSH	X																	
HIV	X																	
Hepatitis C antibody testing	X																	
Hepatitis B testing (HBsAg, HBcAb, HBsAb)	X																	

Visit	Screening		Blinded, Placebo- Controlled Treatment Part A										Open-label Part B				ET	Follow-up Part Ca
	1	1a	2	3	4	5	6	7	8	9	10	11	12	13	14	15		
Week of Treatment			Base-line 0	1	2	4	8	12	14	16	20	24	28	32	40	52	Any week	
Days from Visit 2	-42 to -3 days		0	7 ± 2 days	14 ± 2 days	28 ± 2 days	56 ± 3 days	84 ± 3 days	98 ± 3 days	112 ± 3 days	140 ± 3 days	168 ± 3 days	196 ± 3 days	224 ± 5 days	280 ± 5 days	365 ± 5 days	Any day	28 ± 5 days after last dose
Serum pregnancy test ^m	X		X															
Urine pregnancy test ^m			X	X	X	X	X	X	X	X	X	X	X	X	X	X	X	X
FSH ⁿ	X																	
Clinical chemistry ^o	X		X	X	X	X	X	X	X	X	X	X	X	X	X	X	X	X
Lipid panel ^p			X					X				X				X		
Lipid NMR ^q			X					X										
Hematology	X		X	X	X	X	X	X	X	X	X	X	X	X	X	X	X	X
HBV DNA ^r								X				X		X	X	X	X ^s	
Iron studies (iron, TIBC, and ferritin)	X		X					X				X				X		
Urinalysis	X		X					X				X		X		X	X	
Rheumatoid factor	X		X					X				X				X	X	
hsCRP	X		X	X	X	X	X	X	X	X	X	X	X	X	X	X	X	X
Erythrocyte sedimentation rate ^t	X		X	X	X	X	X	X	X	X	X	X	X	X	X	X	X	X
Anti-CCP	X		X					X				X				X	X	
Immunoglobulin levels (IgG, IgA, IgM)	X		X			X		X				X				X	X	
Lymphocyte subsets (T, B, NK, and T-cell subsets)	X		X			X		X				X				X	X	
Exploratory storage samples (serum and plasma)			X	X	X	X		X				X				X		

Visit	Screening		Blinded, Placebo- Controlled Treatment Part A										Open-label Part B				ET	Follow-up Part Ca
	1	1a	2	3	4	5	6	7	8	9	10	11	12	13	14	15		
Week of Treatment			Base-line 0	1	2	4	8	12	14	16	20	24	28	32	40	52	Any week	
Days from Visit 2	-42 to -3 days		0	7 ± 2 days	14 ± 2 days	28 ± 2 days	56 ± 3 days	84 ± 3 days	98 ± 3 days	112 ± 3 days	140 ± 3 days	168 ± 3 days	196 ± 3 days	224 ± 5 days	280 ± 5 days	365 ± 5 days	Any day	28 ± 5 days after last dose
Exploratory storage samples (urine)			X	X	X	X		X				X					X	
Exploratory storage samples (RNA)			X	X	X	X		X				X					X	
DNA collection			X									X						

Abbreviations: Anti-CCP = anticyclic citrullinated peptide; BP = blood pressure; DNA = deoxyribonucleic acid; eGFR = estimated glomerular filtration rate; EQ-5D-5L = European Quality of Life-5 Dimensions-5 Level; ET = early termination; FACIT-F = Functional Assessment of Chronic Illness Therapy Fatigue scale; FSH = follicle-stimulating hormone; HAQ-DI = Health Assessment Questionnaire-Disability Index; HBcAb = hepatitis B core antibody; HBsAb = hepatitis B surface antibody; HBsAg = hepatitis B surface antigen; HBV DNA = hepatitis B virus deoxyribonucleic acid; HIV = human immunodeficiency virus; hsCRP = high-sensitivity C-reactive protein; Ig = immunoglobulin; IWRS = interactive web-response system; NK = natural killer; NMR = nuclear magnetic resonance; NRS = numeric rating scale; PPD = purified protein derivative; QIDS-SR16 = Quick Inventory of Depressive Symptomatology-Self-Rated (16 items); RA = rheumatoid arthritis; RNA = ribonucleic acid; TB = tuberculosis; TIBC = total iron binding capacity; TSH = thyroid stimulating hormone; WPAI-RA = Work Productivity and Activity Impairment-Rheumatoid Arthritis.

- Those patients who complete the study and do not enroll in extension Study JADY should return for a safety follow-up visit 28 days after their last dose of study drug. Those patients who do enroll in Study JADY do not need to return for a follow-up visit.
- Symptom-directed physical examinations may be conducted at the investigator's discretion at any visit and any time a patient presents with physical complaints.
- Include recording of habits such as caffeine, alcohol, and tobacco consumption.
- Electrocardiograms will be performed locally and will be locally (machine) read.

- e If the PPD test is positive and the patient has no medical history or chest x-ray findings consistent with active TB, the patient may have a QuantiFERON TB Gold or T-SPOT.TB test (if available). If the QuantiFERON-TB Gold or T-SPOT.TB test results are not negative, the patient will be considered to have latent TB. If the QuantiFERON-TB Gold or T-SPOT.TB test is available and in the judgment of the investigator, preferred as an alternative to the PPD skin test for the evaluation of TB infection, it may be used instead of the PPD TB test. If the QuantiFERON-TB Gold or T-SPOT.TB test is positive, the patient will be considered to have latent TB. If the test is not negative, the test may be repeated once within 2 approximately weeks of the initial value. If the repeat test results are again not negative, the patient will be considered to have latent TB.
- f A chest x-ray will be taken locally at screening unless one has been obtained within the past 6 months (provided the x-ray and/or report are available for review).
- g At Visit 2, the patient will take his/her oral investigational product at the clinic under the supervision of study staff.
- h At Visits 3, 4, and 8, patients should bring their investigational product with them to the study visit, but no tablet counts need to be performed.
- i All the radiographic images of the hands and feet will be submitted to the central reader for reviewing. At screening, radiographic images of the hands and feet acquired within 4 weeks prior to study entry may be submitted to the central reader to confirm eligibility. If a patient undergoes rescreening, radiographic images acquired as part of initial screening and within 10 weeks of randomization may be used.
- j X-rays will only be taken at early termination if the most recent x-ray was more than 12 weeks earlier.
- k Morning joint stiffness, Worst Tiredness, and Worst Joint Pain assessments will be collected using paper patient diary through Week 12 to assess duration, severity of morning joint stiffness, recurrence of stiffness during the day, worst tiredness and worst joint pain.
- l Morning joint stiffness duration, Worst Tiredness, and Worst Joint Pain assessments will be collected using an electronic patient-reported outcomes [ePRO] tablet at each visit.
- m For all women of childbearing potential, a serum pregnancy test (central laboratory) will be performed at Visit 1 and Visit 2. Urine pregnancy tests (local laboratory) will also be performed at Visit 2 and at all subsequent study visits.
- n To confirm postmenopausal status for women ≥ 40 and < 60 years of age who have had a cessation of menses, an FSH test will be performed. Nonchildbearing potential will be defined as an FSH ≥ 40 mIU/mL and a cessation of menses for at least 12 months.
- o Clinical chemistry will include the following values calculated from serum creatinine: calculated creatinine clearance (Cockcroft-Gault equation) and eGFR (calculated using the Modification of Diet in Renal Disease isotope dilution mass spectrometry traceable method).
- p Fasting lipid profile. Patients should not eat or drink anything except water for 12 hours prior to sample collection. If a patient attends these visits in a nonfasting state, this will not be considered a protocol violation.
- q Lipid NMR tests will not be performed at sites in China. Other participated countries will have this tests.
- r HBV DNA monitoring will be performed in patients who tested positive for HBcAb at screening.
- s To be performed only if previous test was more than 3 months earlier.
- t Erythrocyte sedimentation rate will be performed locally using a kit provided by the sponsor.

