7.2. Discussion of Design and Control

Based on efficacy, safety, and pharmacokinetic (PK) data from the Phase 2 studies (JADC and JADA), Eli Lilly and Company (Lilly) has selected a single dose of 4 mg QD baricitinib (with dose adjustment for renal dysfunction) for evaluation in this study (see Section 9.4 for rationale).

The Week 12 primary efficacy endpoint was chosen based on the results of Studies JADC and JADA. In these studies, efficacy as measured by ACR20 response was observed as early as 2 weeks after initial administration of baricitinib followed by near-maximum efficacy response achieved by Week 12. The 52-week treatment period will allow evaluation of the long-term effect of baricitinib on structural joint damage.

All patients will be required to be on background MTX treatment at baseline. Other background therapies, including NSAIDs and low dose oral corticosteroids, are permitted during the study

for patients who are on stable doses of these treatments at baseline. Patients should remain on the same dose of MTX throughout the study; however, the MTX dose may be adjusted for safety reasons.

To prevent potential unblinding due to observed efficacy or laboratory changes, a “dual assessor” approach will be used to evaluate efficacy and safety. The Joint Assessor (or designee) should be a rheumatologist or skilled arthritis assessor. The Joint Assessor will be responsible for completing the joint counts. To ensure consistent joint evaluation throughout the trial, individual patients should be evaluated by the same Joint Assessor for all study visits. The Joint Assessor must not access or discuss with the patient the patient-reported assessments, Physician’s Global Assessment of Disease Activity (visual analog scale [VAS]), and safety assessments.

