The Safety Assessor (or designee) should be a rheumatologist (or medically qualified physician) and will have access to both safety and efficacy data. The Safety Assessor may be the Principal Investigator (PI). The Safety Assessor will be responsible for completing the Physician’s Global Assessment of Disease Activity (VAS). To ensure consistent Physician’s Global Assessment of Disease Activity (VAS) throughout the trial, the instrument should be evaluated by the same physician at all study visits. The Safety Assessor will have access to source documents, laboratory results, and case report forms (CRFs) and will be responsible for making treatment decisions based on a patient’s clinical response and laboratory parameters.

All patients in Study JAGS will be offered rescue therapy starting at Week 16 in line with precedent from recent clinical trials. Patients who are determined to be nonresponders to their originally assigned treatment will be reassigned to treatment with baricitinib at Week 16. Patients originally assigned to baricitinib will be rescued to the same dose of baricitinib to maintain the study blind. Patients not rescued at Week 16 may be rescued to treatment with baricitinib at the discretion of the investigator anytime thereafter. Patients initially randomized to placebo and not rescued will be reassigned to receive baricitinib at Week 24 to limit exposure to inactive treatment. Patients not experiencing improvement in signs and symptoms following approximately 4 weeks of rescue treatment should be discontinued from the study. Patients may be rescued only once. See Section [9.5.1](#) for details of rescue treatment.

8. Study Population

The study population will be comprised of patients diagnosed with RA with active disease who have failed to adequately respond to MTX. Study investigator(s) will review patient records and screening test results to determine that the patient meets all inclusion and exclusion criteria to qualify for participation in the study.

Individuals who do not meet the criteria for participation in this study (screen failure) may be re-screened. Individuals may be re-screened up to 1 time. The interval between re-screenings should be approximately 30 days. Each time re-screening is performed, the individual must sign a new informed consent form (ICF) and will be assigned a new identification number.

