9.4. Rationale for Selection of Doses in the Study

Clinical Efficacy Considerations

A single initial dose of 4 mg QD baricitinib in this study was selected based on the efficacy, safety, and PK data from Phase 2 Studies JADC and JADA. In Study JADC, baricitinib doses of 4, 7, and 10 mg QD were studied and found to produce similar degrees of efficacy across the measured parameters at both the Week 12 and Week 24 time points. Study JADA included lower doses of baricitinib (1 and 2 mg QD) to find the minimum clinically effective dose and to confirm the flat dose-response curve in the dose range of 4 to 8 mg QD. In Study JADA, a relatively flat dose-response curve was observed in the 4- and 8-mg QD dose groups at Week 12 across almost all measured efficacy parameters. The 1- and 2-mg QD dose groups are biologically active but did not produce adequate response at Week 12 as assessed by ACR50, ACR70, and low disease activity and remission rates when compared to placebo and the 4- and 8-mg dose groups. All 4 doses were associated with reductions in hsCRP and ESR values over time. Assessment of the Week 12 magnetic resonance imaging (MRI) data suggests the potential for the 4- and 8-mg QD baricitinib doses to have a favorable impact on reducing structural damage given the observed significant improvement in osteitis.

Week 24 data from Study JADA demonstrated persistence of the flat dose response between the 4- and 8-mg QD doses. Over the second 12-week period, continued administration of the 2-mg QD dose did not result in further improvement in the clinically important endpoints of ACR50, ACR70, DAS28-hsCRP ≤ 3.2 , DAS28-hsCRP < 2.6 , and CDAI and SDAI remission rates. Week 24 MRI data further support the potential for the 4- and 8-mg QD doses to have a beneficial effect on prevention of structural damage.

Clinical Safety Considerations

Baricitinib was generally safe and well tolerated in single doses ranging from 1 to 20 mg and in repeat oral doses ranging from 2 to 20 mg. The most commonly reported treatment-emergent

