10.4.1. Samples for Standard Laboratory Testing

Standard laboratory tests, including chemistry, hematology, and urinalysis panels, will be performed. Specifically, hsCRP results will be blinded after Visit 2. Serum and/or urine pregnancy tests will be performed at each visit as described in the study schedule ([Attachment 1](#)). Blood and urine samples will be collected for other laboratory tests at the times specified in the study schedule ([Attachment 1](#)). Blood will be collected by venipuncture. [Attachment 2](#) lists the specific tests that will be performed for this study.

Routine and other clinical laboratory tests will be analyzed by a central laboratory selected by Lilly.

Investigators must document their review of each laboratory safety report.

Samples collected for specified laboratory tests will be destroyed within 60 days of receipt of confirmed test results. Tests are run and confirmed promptly whenever scientifically appropriate. When scientific circumstances warrant, however, it is acceptable to retain samples to batch the tests run or to retain the samples until the end of the study to confirm that the results are valid. Certain samples may be retained for a longer period, if necessary, to comply with applicable laws, regulations, or laboratory certification standards.

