- k ESR analysis will be performed by the local laboratory.

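### hsCRP is blinded after Visit 2, but nothing in the plan keeps the locally run ESR from the physician who scores the Physician's Global Assessment

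*Protocol*

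**What the plan says.** Protocol Section 7.2 sets up two assessors with a stated aim: "To prevent potential unblinding due to observed efficacy or laboratory changes". The Joint Assessor does the joint counts and is kept away from patient-reported, physician-global and safety assessments. The Safety Assessor is placed on the other side of that line: "The Safety Assessor will have access to source documents, laboratory results, and case report forms (CRFs". The same person scores the Physician's Global Assessment, and Section 7.2 asks that one physician do so at all visits.

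Protocol Section 10.4.1 masks one acute-phase marker: "Specifically, hsCRP results will be blinded after Visit 2". For ESR, the schedule in Attachment 1 marks Visit 1, Visits 2 to 15, early termination and follow-up. Its footnote says "Erythrocyte sedimentation rate will be performed locally using a kit provided by the sponsor", and Attachment 2 says "ESR analysis will be performed by the local laboratory". Neither the protocol nor the SAP masks ESR or routes it away from an assessor.

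On Phase 2, protocol Section 9.4 reports: "All 4 doses were associated with reductions in hsCRP and ESR values over time".

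**The concern.** The Physician's Global is a subjective scale. A physician who watches ESR fall from baseline may suspect active drug and rate disease activity lower. One who sees it stay high may do the reverse. Such a bias would favour baricitinib. It would act on ACR20 at Week 12 (primary endpoint) and on SDAI ≤3.3 at Week 12 (secondary), and on CDAI among the exploratory measures. ESR is not itself a component of any of these three, so the only route is through the rating. The exposure matters in Part A; Part B is open-label.

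The plan blinds hsCRP and leaves open a second marker of the same process, although it states that both fell on drug.

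**Working it through.** **Step 1: access, with the passages side by side**

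| Link | Source | hsCRP | ESR |
|---|---|---|---|
| Where run | Protocol 10.4.1, Attachments 1 and 2 | Central laboratory | Locally |
| Measured at Week 12 | Attachment 1 | Yes | Yes |
| Fell on drug in Phase 2 | Protocol 9.4 | Yes | Yes |
| Masked after Visit 2 | Protocol 10.4.1 | Yes | No statement |
| Inside the Safety Assessor's stated access | Protocol 7.2 | Removed by the masking | Not removed |

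No sentence requires the Global to be scored before results are seen. SAP Section 6.1.1 accepts a baseline Global recorded up to 5 days after first dose, so same-day entry is not assumed even at baseline.

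**Step 2: the plan's own figure**

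Protocol Section 12.1 gives 60% versus 35%, 144 per arm, two-sided 0.05, power 99%. With pooled rate 0.475:

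- SE under no difference = √(2 × 0.475 × 0.525 / 144) = 0.0589
- SE under the planned rates = √((0.60 × 0.40 + 0.35 × 0.65) / 144) = 0.0570
- Power = Φ((0.25 − 1.96 × 0.0589) / 0.0570) = Φ(2.36) = 99.1%

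The stated power is reproduced.

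**Step 3: how many patients the Global could tip into response**

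ACR20 needs both joint counts plus at least 3 of 5 items. Among patients who pass both joint counts, a biased Global creates a response only if exactly 2 of the other 4 items pass and the unbiased Global would have failed.

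Assumptions, none from the documents: each item passes with probability q = 0.5 to 0.7, and latent correlation is 0.5 between items. Given a shared normal factor u, each item passes with probability c(u) = Φ((Φ⁻¹(q) + √0.5·u) / √0.5). The pool is the average over u of 6c²(1 − c)³.

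| q | Exactly 2 of 4 pass | …and the Global fails (the pool) |
|---|---|---|
| 0.5 | 20.0% | 10.0% |
| 0.6 | 19.1% | 8.9% |
| 0.7 | 16.4% | 7.0% |

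If 5-20% of the pool is tipped (assumed), ACR20 in this group moves by 0.05 × 7.0% = 0.35 points to 0.20 × 10.0% = 2.0 points. If 50-80% of an arm passes both joint counts (assumed), the shift over the whole arm is 0.5 × 0.35 = 0.2 to 0.8 × 2.0 = 1.6 points.

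The result depends on the correlation. With independent items the pool is 6q²(1 − q)³ = 18.8%, 13.8% and 7.9% at the same three rates. Independence is unlikely for five measures of one disease.

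**Step 4: what a shift of that order would do**

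By the Step 2 formula, removing 2 points from the planned 60% leaves power at 97.8%. If there were no true effect at a 35% rate, a 2-point bias would give a 5.4% chance of a significant result favouring baricitinib, against 2.5% nominal in that direction.

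**Step 5: SDAI**

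The Global enters SDAI point for point. An assumed shift of 0.5 cm is 0.5 / 3.3 = 15% of the remission cut-off.

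**The case against.** The other side has real force.

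- **Access is inferred.** No passage says ESR is reported to the Safety Assessor, and a laboratory manual outside these documents could mask it. This stands: the text supports only that the protocol does not protect ESR.
- **The design is disclosed.** Section 7.2 openly gives the Safety Assessor efficacy data, laboratory results and the Global. The joint counts, which are mandatory for ACR20, belong to the other assessor. This limits the damage but does not explain why one acute-phase marker is blinded and the other is not.
- **ESR is one part of a wider exposure.** The same physician sees hemoglobin, neutrophils, platelets and lipids, which Sections 5 and 9.4 say change on drug. This stands. Those results, however, serve safety monitoring; ESR is in no interruption, stopping or rescue rule.
- **A fall in ESR does not reveal the arm.** It can fall in a placebo patient who improves, and a lower Global may then be a fair rating. This also stands; the risk is expectation bias, not disclosure of allocation.

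A reader might infer three stronger claims that the documents do not support:

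1. That hsCRP was blinded to protect the Global. Section 10.4.1 gives no reason; the purpose stated in Section 7.2 belongs to the dual-assessor approach.
2. That blinding hsCRP is useless while ESR is visible. Nothing in either document shows this.
3. That ACR20 would move by 1-4 points. That figure applies 5-20% to all 16-20% of patients with exactly 2 of 4 items improved, including those whose Global already passes. It could arise only as a between-arm difference, with placebo patients tipped downward at a like rate.

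**Conclusion.** The gap is real and specific: the protocol leaves a drug-responsive disease-activity marker open to the physician who makes a subjective rating that enters the primary endpoint and a secondary one. It does not show that the rater sees ESR or that the blind is broken.

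The size cannot be estimated from the documents. The figure of about 0.4-2 points in ACR20 among patients meeting both joint-count criteria rests on assumed item rates, correlation and tipping rate. A shift of that order could not produce the planned 25-point difference. It bears on the credibility of the estimate, and more so for SDAI, where the Global counts directly against a low cut-off. The point merits a cheap procedural correction and does not threaten the trial's main conclusion.

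**What to change.** Add to protocol Section 10.4.1 and to the site instructions:

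1. Post-baseline ESR values are withheld from the Joint Assessor and from the physician rating the Global through Visit 11. The local laboratory or existing staff enter them directly.
2. At each Part A visit the Global is entered before that visit's laboratory results are opened. Section 11.1 already has it entered directly into the electronic system.

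If a laboratory manual already masks ESR, one protocol sentence saying so settles the first item.

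**Cost.** A protocol sentence and a site instruction, with no change to sample size or analysis. The entry order needs no added staff; the withholding relies on someone other than the two assessors handling the result. Physicians would not see ESR in Part A. Tables JAGS.8.1 and JAGS.8.2 do not use it, and rescue under Section 9.5.1 rests on joint counts. DAS28-ESR is exploratory and can still be computed.

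**Limit.** Hematology and lipid results from earlier visits must stay visible for safety, so the exposure is narrowed and not closed.
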